Patients will be excluded from participation if they meet any of the following criteria: (1) diagnosis of cancer or any other malignant disease, (2) acute osteomyelitis or acute bone disease, (3) present or past DSM-V diagnosis of schizophrenia, delusional disorder, psychotic disorder, or dissociative disorder that would be judged to interfere with study participation, (4) pregnancy, (5) any clinically unstable systemic illness judged to interfere with treatment, (6) a pain condition requiring urgent surgery, (7) an active substance use disorder, such as cocaine or IV heroin use (positive on the Mini International Neuropsychiatric Interview; M.I.N.I. v.5.0), that would interfere with study participation, and (8) have an implanted cardiac pacemaker, defibrillator, or other implanted device. All subjects will be asked to not change their treatment during the study period, (9) Raynaud's syndrome, or (10) Open cuts/sores.

Patients will be equally randomized to one of two experimental groups in this trial (i.e., Active Quell or Sham Quell) with the goal of having 50 subjects complete the trial in each group. The Sham Quell will look exactly like the Active Quell but will be programmed to give 2 minutes of stimulation three times during the 1-hour therapy session (2 minutes of stimulation at 0, 28, and 58 minutes, etc.). Subjects will be told that they will be exposed to two treatment conditions, lower intensity or higher intensity stimulation, and will be asked to use the device (standard or sham) every day for 12 weeks. Neither the investigators nor the study participants will know for sure which device they will be receiving. All subjects will complete assessment measures and be followed for 3 months. Recruitment will not be

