All subjects (Quell and Sham Quell condition) will be encouraged to use their assigned device for at least 3 therapy sessions (3 hours of stimulation) every day, and to wear the device as often as possible, including while sleeping. Tracking of use of the device will be available electronically through the Quell Relief mobile app (subject data will be de-identified on the Quell server). All demographic and daily pain assessment data will be stored on a secure server (Mass General Brigham Amazon Web Server - MGB AWS) using the Veracode-tested study pain app and portal. Messages will be sent via the 2-way messaging pain app program to help track use of the device and to monitor and encourage active participation. Subjects will be instructed to enter daily assessments only when they are wearing the Quell device. Patients who wish to discontinue the study will be allowed to do so at their request. If the participant is willing, we will meet with her or him to understand reasons for discontinuing the study and problem-solve to see if there would be a way to keep following the individual. All subjects will be asked to complete a packet of questionnaires at the conclusion of the first 6-week study phase and then at the 3-month mark. All subjects will also be asked to participate in the full QST session described below at baseline, and then again at the end of the study (i.e., QST will be completed at the same poststudy visit when outcome measures are collected). Each subject will be compensated \$50 at baseline, \$25 mid study, and \$100 at study completion upon receipt of their completed questionnaires for a possible total of \$175. At the end of the study subjects will be informed which device was the standard Quell device and they will be encouraged to keep this device for future use. Those in the Sham treatment arm will be offered a standard Quell for use after the study. It is expected that 15% of the subjects will dropout before completing the trial and recruitment of a total of 115 subjects may likely be needed to successfully complete the study.

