Quantitative Sensory Testing (QST) Protocol: All subjects will be administered a battery of sensory assessment measures at baseline and again at the end of the 3-month study. A list of the QST measurements used in this proposed study is presented in Table 2. We will assess mechanical pain assessment and cold pain assessment. For mechanical pain, responses to punctate mechanical stimuli will be measured using a standard set of weighted probes (pinprick stimulators) that provides estimates of pain threshold and mechanical temporal summation. Singular taps will be performed on the metacarpophalangeal joint of the middle finger of the non-dominant hand using these probes (*Touch-Test Sensory Evaluator; www.ncmedical.com*) developed by the German Research Network (Backonja, 2009). The lowest-force stimulator that produces a sensation of discomfort at the level 10 out of a 100-point scale will then be used to assess the temporal summation of pain that occurs with rapid administration of identical stimuli for a series of 10 pinpricks (with 1-second inter-stimulus intervals). Participants will be asked to rate the painfulness of the first, fifth, and tenth stimulus; mechanical temporal summation will be defined as the increase in pain from the first to the final stimulus. A Somedic pressure algometer will be utilized to assess responses to pressure stimulation at several

anatomical sites. Pain pressure thresholds (PPT) will be determined twice on the right and left sides of the body: the trapezius, and thumb joint. Mechanical pressure will be applied using a 0.5-cm² probe covered with 1mm polypropylene pressure-transducing material; pressure will be increased at a steady rate of 30 kPA/s until the subject indicates that the pressure is painful. Finally, we will use cuff algometry to assess responses to sustained mechanical pressure. A Hokanson rapid cuff inflator will be used to inflate a standard blood pressure cuff around the gastrocnemius muscle of the dominant leg until the subject indicates a pain level was 40 out of a 100-point scale. This pressure will be used in the next test and will not be changed. Over the course of 2 minutes, at 30 second intervals, the subject will be asked to rate her or his current pain level on a scale 0 to 100. As with each of these psychophysical testing procedures, participants will be informed that they could terminate the procedure at any time.

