Blinding: The proposed randomization ratio will be 1:1 Active to Sham device. The Sham device is identical to the Active Quell in all aspects with one exception. While the Active Quell typically delivers 1 hour of continuous stimulation during a therapy session, the Sham Quell device will deliver only three 2minute periods of stimulation (at 0, 28 and 58 minutes) within each 60-minute therapeutic session. Recent studies suggests that this limited stimulation offers some perceived analgesic effect (Jamison, Edwards et al., 2021; Jamison, Curran et al., 2021). The subjects will be informed that they will be receiving either low or high intensity therapy. Neither the principal investigator, the co-investigators, the research assistant (RA, who will serve as the study coordinator), nor the subjects will know if they are given a sham device or the actual Quell device. The devices will be randomly numbered and provided by NeuroMetrix and information about the device assignment will be managed through NeuroMetrix. At the end of 6 weeks and again after 3 months, subjects will be asked if they thought they had the Sham (low intensity) Quell or (high intensity) Active Quell device. The co-principal investigators and the RA will be asked to identify which subjects they thought had Active Quell vs the Sham Quell device prior to analyses of the data. Both the Active Quell and the Sham Quell will communicate via Bluetooth with the same mobile application. This application provides the subjects with a dashboard of device information, trending data on device usage, and sleep quality. This same information will be synced to a cloud database so that investigators involved in the study can collect these data remotely, as well as monitor

adherence with the device. In a past unpublished investigation when this blinding procedure was used among 17 subjects and 11 physicians, investigators accurately guessed the device (sham or active) a subject was randomized to in 11 of 17 participants (64.7%). Eleven of 17 (64.7%) study participants accurately guessed the device to which they were randomized. However, in a recent randomized study in which subjects were assigned to either an Active or Sham Quell device, most of the subjects (84.9%) believed that they had been assigned to the Sham Quell device (Jamison, Edwards et al., 2021; Jamison, Curran et al., 2021).

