Research Objectives: This study is expected to take 18-24 months to complete and is designed to gather information about the use of the Quell for persons with COPCs. We hypothesize that those using the Active Quell device will report reduced pain compared with the Sham Quell condition. We also expect that those using the active device will show improvement in sleep, mood, and level of activity over the 3-months of using the device. We hypothesize that frequency of using the Quell (increased tolerability and adherence) will be correlated with greater reduction in pain. We hypothesize that the device will be safe to use and will demonstrate a reduction in healthcare utilization (reduced clinic and ED visits). We will also investigate use of prescription opioids and other nonopioid pain medications among the study subjects and determine the effect of daily use of the Active Quell (vs. Sham Quell) on intake of prescription pain medication. Finally, based on preliminary analyses from prior Quell studies, we will investigate whether certain individuals report greater benefit from using the Active Quell than others and, in particular, we predict that those with more pain sensitivity and longer duration of pain will demonstrate most benefit from the Active Quell. The previous studies in LBP and fibromyalgia patients both yielded evidence that the most pain-sensitive patients reported the greatest reductions in pain with Active Quell use. In the present proposal, we will be recruiting participants with evidence of sensitization at baseline and we will evaluate whether the most-sensitized patients with COPCs, even within a generally sensitized group of patients, show the greatest analgesic benefits. We will examine trends from the daily pain ratings on the pain app since it gives multiple daily pain ratings over the course of the study. We will target the 7-item activity interference subscale of the BPI (0=does not interfere; 10=completely interferes) as the primary outcome, and the PCS, PDI, HADS, painDETECT, SIQR, PGIC, healthcare utilization, and satisfaction questions as secondary outcome measures.

Statistical POW

Power calculations, as outlined by Cohen (1988), were performed to determine the probability of detecting clinically significant differences between treatment conditions in the primary area of measurement. These calculations assumed a two-tailed test and alpha level of 0.05 confirming the

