Multivariate imputation with chained equations (MICE) will be used to fill in missing assessments (including for subjects that drop out). MICE is valid under the assumption that data is missing at random (MAR). Variables will be modeled using normal regression. For each efficacy measure, the imputation model will include the available baseline, week-6 and 3-month data, demographics (age, BMI, education) and pain characteristics. The active and sham groups will be separately imputed. The same random-number seed will be used for computation of 250 complete (i.e., no missing data) datasets for each efficacy measure. For each dataset, the 3-month least-square mean change scores will be determined. The results will then be combined according to Rubin's rule. A sensitivity analysis for data missing not at random (MNAR) rather than MAR will be performed using delta-based MI. Specifically, the LS mean change scores will be reanalyzed with deterministic increases to the 3-month assessments (i.e., smaller change scores) of subjects on active treatment that withdrew from the study.

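### The imputation model does not name baseline QST sensitivity, the planned predictor of benefit; if the sensitivity-by-treatment question is tested on the imputed change scores, the interaction shrinks by up to about the missing share

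*Combined protocol and SAP*

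**What the plan says.** The missing-data paragraph, which follows the power section, gives multiple imputation by chained equations as the only method for missing assessments, dropouts included. On the predictors it says that "the imputation model will include the available baseline, week-6 and 3-month data, demographics (age, BMI, education) and pain characteristics". The arms are imputed separately. The one stated use of the completed datasets is the 3-month least-squares mean change score for each efficacy measure, pooled by Rubin's rule, with a delta-adjusted sensitivity analysis of the same scores.

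Research Objectives makes a prediction about who benefits: "we predict that those with more pain sensitivity and longer duration of pain will demonstrate most benefit from the Active Quell". It adds that "we will evaluate whether the most-sensitized patients with COPCs, even within a generally sensitized group of patients, show the greatest analgesic benefits". It gives no model, outcome or dataset for this.

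The QST Protocol section states that "All subjects will be administered a battery of sensory assessment measures at baseline and again at the end of the 3-month study". The baseline measure is therefore available for people who later drop out.

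On missing data, Research Design and Methods says that "It is expected that 15% of the subjects will dropout before completing the trial" and that "recruitment of a total of 115 subjects may likely be needed to successfully complete the study", "with the goal of having 50 subjects complete the trial in each group". The Blinding section sets the allocation: "The proposed randomization ratio will be 1:1 Active to Sham device".

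**The concern.** An imputation model should contain the variables of any analysis run on its output. If QST is absent, an imputed 3-month score is related to the patient's sensitivity only through whatever the included variables carry. Observed patients keep the true slope of change on QST, and imputed patients get a flatter one. The pooled slope is diluted in each arm, and so is the difference between the arms. Separate imputation protects the arm means, but it does not put a QST slope into data imputed without QST.

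At stake is the plan's own question of whether sensitivity modifies benefit. The contrast is already hard to see, because everyone enrolled must meet a QST hypersensitivity cutoff.

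**Working it through.** **Missing share, m.** The plan's recruitment figure reproduces as 100 × 1.15 = 115. Dividing by the retention rate gives 100 / 0.85 = 117.6, or 118.
- 115 recruited and 50 completers per arm: m = 15/115 = 13.0%.
- The stated dropout rate: m = 15%, leaving 115 × 0.85 = 97.75 completers.
- Whole patients, 9 of 57 per arm: m = 15.8%.

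**Formula.** Let β be the true QST slope in an arm and s the share of it that the included predictors reproduce. If dropout is unrelated to QST, the slope in the completed data is (1 − m)β + m·sβ = β[1 − m(1 − s)]. The loss is m(1 − s). The same factor applies in each arm, so it applies to the difference in slopes.

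**No dropout has week-6 data, and nothing else carries QST (s = 0).** The loss equals m: 13.0%, 15% or 15.8%. For an assumed interaction of 0.6 points per SD of QST, that is 0.6 × 0.130 = 0.078 to 0.6 × 0.158 = 0.095 points.

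**All dropouts have week-6 data.** The documents give no correlation between QST, week 6 and month 3, so these are assumptions. Let f be the share of the QST effect present at week 6 and r the residual correlation of week 6 with month 3. Take residual SD 1.8 (the power section's SD) and slope 0.6. Given baseline, the week-6 coefficient is (0.36f + 3.24r) / (0.36f² + 3.24), and s is f times that.
- f = 0.7, r = 0.6: (0.252 + 1.944) / (0.1764 + 3.24) = 0.643; s = 0.45; loss = 0.15 × 0.55 = 8.3%.
- f = 1, r = 0.8: (0.36 + 2.592) / (0.36 + 3.24) = 0.82; s = 0.82; loss = 0.15 × 0.18 = 2.7%.

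Weaker assumed correlations, at m = 15.8%, took the loss to 11%.

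**Simulation check** (400,000 per arm, normal-regression imputation by arm, slope of change on QST adjusted for baseline, m = 15%, dropout unrelated to QST):

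| Dropouts with week-6 data | f = 0.7, r = 0.6 | f = 1, r = 0.8 |
|---|---|---|
| None | 14.2% | 15.2% |
| Half | 11.9% | 8.5% |
| All | 8.1% | 2.6% |

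The formula and the simulation agree. Further settings:
- Pain characteristics includes a proxy correlated 0.5 with QST (assumed): s = 0.25 and the loss is 0.15 × 0.75 = 11.3% with no week-6 data (simulated 10.9%). With half having week-6 data it is 8.8%.
- Dropout itself depends on QST (assumed): 9% to 19%.
- Baseline QST added to each arm's model: −0.8% to +1.0% across all settings, which is simulation noise.

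**Against sampling error.** With 50 per arm, SD 1.8 and a standardised moderator, the interaction's standard error is 1.8 × √(2/50) = 0.36. An interaction of 0.6 is 0.6/0.36 = 1.67 standard errors, or about 38% power. A bias of 0.078 to 0.095 points is 0.22 to 0.26 standard errors. In trial-sized simulations (57 per arm, 7 to 9 missing, interaction 0.6), leaving QST out lowered power from about 39% to between 26% and 33%.

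**The case against.** The strongest reply is that nothing sends the moderator question through the imputed data. Their stated use is least-squares mean change. Research Objectives speaks of analgesic benefit and then turns to the daily app ratings, and the power section plans multi-level models of those ratings, which need no imputation step. This stands, so the point is conditional. It does not dispose of the point: imputation is the only missing-data method given, it covers each efficacy measure, and the power section says most analyses will use change scores. Testing moderation on the completed change scores is a natural reading that the plan leaves open.

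Second, pain characteristics is undefined and could include QST or, more naturally, pain duration. That also stands. A reader might infer that QST is definitely excluded, and the documents do not show that. They show only that it is not named.

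Third, a reader might infer that dropping the missing patients would simply do better. That holds for average bias only. In a simulation with 57 per arm, 15.8% missing at random, week-6 data for all and residual SD 1.7, the root mean squared error was 0.324 imputed without QST, 0.353 imputed with QST and 0.363 for complete cases. Leaving QST out gives a less variable estimate, but one shrunk towards zero, with less power for the question.

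Fourth, the bias is conservative and small beside sampling error, and the question is investigative. All true, and it limits the weight of the point.

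**Conclusion.** The point holds conditionally. If baseline QST is left out of the imputation model, and the sensitivity-by-treatment interaction is estimated on the imputed change scores, it is pulled towards zero. With dropout unrelated to QST, the ceiling is about the missing share: 13% at 15/115, and 15% to 16% at the expected dropout. If all dropouts have week-6 data the loss is roughly 3% to 11%, depending on correlations the documents do not give. Lower attrition would shrink it: at 5% missing, the loss is 1% to 5%.

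Two stronger readings are not supported. One is that every test of the prediction is biased by a fixed percentage: the percentages rest on assumptions, and a complete-case or daily-rating analysis would not carry this bias. The other is that the primary comparison is compromised. The arm means are imputed within arm and are largely unaffected. Even with dropout assumed to depend on QST, the main contrast moved by about 0.05 points against an assumed true 1.5, or 3%.

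This is a worthwhile, low-cost improvement to a secondary question.

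**What to change.** In the missing-data paragraph, name one summary baseline QST sensitivity index and pain duration as predictors in each arm's imputation model. Use the same index as the moderator analysis in Research Objectives, and define what else pain characteristics covers. State that the moderator analysis of questionnaire change scores uses these imputed datasets. Because the arms are imputed separately, each arm then keeps its own QST slope.

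The cost is a sentence or two in the plan and no new data collection. The downside is one or two more predictors in a model fitted to about 50 observed patients per arm, and a slightly more variable interaction estimate. A single summary index, rather than the whole QST battery, keeps that cost small.

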Patient Measures: Participants will complete measures recommended by the Initiative on Methods, Measures, and Pain Assessment in Clinical Trials (IMMPACT; Dworkin et al, 2005; Gewandter et al., 2021) as primary outcomes. We will be tracking the patients using validated measures of pain (The Brief Pain Inventory - BPI), coping (Pain Catastrophizing Scale - PCS), level of disability (Pain Disability Index -PDI), mood (Hospital Anxiety and Depression Scale - HADS), presence of neuropathic pain (Pain Detect Neuropathic Pain Questionnaire - painDETECT), pain symptoms and function (Symptom Impact Questionnaire - SIQR), impression of change (Patients' Global Impression of Change - PGIC), healthcare utilization (monthly clinic and ED visits), and overall satisfaction (Satisfaction and qualitative questions developed for this study specifically related to use of a pain management device; see Table 1). We will also track daily ratings of pain, sleep, activity interference, and mood through the pain app. Objective measures of activity, gait, and sleep will be collected by the devices. The 7-item activity interference scale of the Brief Pain Inventory will serve as the primary outcome.

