hypotheses that the Active Quell would be associated with general overall improvement in activity interference on the activity subscale of the Brief Pain Inventory. In our previous work (Jamison, Wan et al., 2019; Jamison, Curran et al., 2021; Jamison, Edwards et al., 2021), we had a high rate of consent to participate among recruited patients, with minimal attrition. We assessed power based on our preliminary data and previously published studies. The power analysis revealed that a sample size of 100 subjects (50 per treatment arm) using a 2-sample t-test for a difference in mean pre/post change score gives the study a >85% probability of detecting a 1.5-point group difference on a 0-10 rating scale (assuming a standard deviation of 1.8). Conventional metrics suggest that a 30% change or difference score is clinically meaningful (Dworkin et al., 2021), and this sample size would provide adequate power to detect a group difference of approximately 20%. Most of the analyses in the proposed study will involve delta scores reflecting changes within subjects (both uncorrected and adjusted - least squares, LS). We also will conduct multi-level modeling analyses of the daily pain assessments. We will examine the distribution of the delta scores between treatment arms and will ascertain whether that distribution is normal. This information will allow us to determine whether parametric (e.g., ANCOVA) or nonparametric analyses should be used. Collectively, this sample size (n=100 total), together with our previously observed very high retention rates and the substantial efficacy of the device, will provide more than adequate power to detect moderate-size effects.

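### The imputation model omits daily app ratings and device-use logs that the trial already collects, so subjects lost before week 6 are imputed from baseline data alone and the primary difference may be biased in either direction

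*Combined protocol and SAP*

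**What the plan says.** The missing-data paragraph, at the end of the statistical power section, fills missing assessments by chained equations under a missing-at-random assumption, with the two arms imputed separately. It states that "the imputation model will include the available baseline, week-6 and 3-month data, demographics (age, BMI, education) and pain characteristics". The term for pain characteristics is not defined. A sensitivity analysis then raises the 3-month scores of withdrawn active-arm subjects by fixed amounts, whose values are not given.

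Other sections show what else will be on file. Patient Measures states: "We will also track daily ratings of pain, sleep, activity interference, and mood through the pain app". Research Design and Methods states: "Tracking of use of the device will be available electronically through the Quell Relief mobile app". The same section places the post-baseline questionnaires at 6 weeks and 3 months only, tells subjects to rate only while wearing the device, and says: "It is expected that 15% of the subjects will dropout before completing the trial". The primary outcome is the BPI activity-interference score. Under Research Objectives, the plan expects more frequent use to go with a larger fall in pain.

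**The concern.** Missing at random is a statement about the variables in the model. For a subject lost before week 6, the week-6 and 3-month questionnaires are both absent, so the chain starts and ends with baseline values, demographics and pain characteristics. The imputed 3-month score is in effect what a same-arm completer with a similar baseline would have had.

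Yet the trial may hold days or weeks of that subject's own ratings, on nearly the same construct as the primary outcome, together with a record of use. The plan's own hypothesis links use to benefit, so these data plausibly predict both leaving and outcome. If they do, and to a different degree in each arm, the primary estimate is shifted although the information to reduce the shift is already on file.

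**Working it through.** **The plan's own figure.** The power section says that 50 per arm "gives the study a >85% probability of detecting a 1.5-point group difference on a 0-10 rating scale (assuming a standard deviation of 1.8"), two-sided alpha 0.05. Standard error = 1.8 × √(2/50) = 0.36. Power = Φ(1.5/0.36 − 1.96) = Φ(2.21) = 98.6% (98.5% with the noncentral t). The stated lower bound holds, and 0.36 serves below as the yardstick for bias.

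**Number affected.** 0.15 × 115 = 17.25, about 17 subjects. The plan does not split dropout by arm, by time or by reason.

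**How the bias arises.** Let p be the proportion of an arm lost before week 6, and g the mean improvement imputed to them minus the mean improvement they truly had. Then

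bias in the difference = p(active) × g(active) − p(sham) × g(sham).

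The sign depends on which product is larger, and the documents give neither p nor g by arm.

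**Size.** From the documents: true difference 1.5, SD 1.8, 15% dropout, imputation by arm. Assumed, because the documents are silent: correlation r of early daily response with 3-month change 0.5 or 0.7; baseline-change correlation 0.3; log-odds of dropout rising by s = 0.5 or 1.0 per point of poorer early response; all or half of the dropout before week 6, with later dropouts adding no bias. The simulation used 1,000,000 subjects per arm, with baseline as the only predictor, as for an early leaver under the listed model. Entries are bias in points; plus favours active.

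| r | s | Lost before week 6 | Selection alike, relative to arm mean | Poor responders leave active only | Poor responders leave sham only | One absolute lack-of-benefit threshold in both arms |
|---|---|---|---|---|---|---|
| 0.5 | 0.5 | 15% | 0.00 | +0.10 | −0.10 | −0.05 |
| 0.5 | 1.0 | 15% | 0.00 | +0.16 | −0.16 | −0.12 |
| 0.7 | 0.5 | 15% | 0.00 | +0.14 | −0.14 | −0.07 |
| 0.7 | 1.0 | 15% | 0.00 | +0.22 | −0.22 | −0.17 |
| 0.5 | 0.5 | 7.5% | 0.00 | +0.05 | −0.05 | −0.03 |
| 0.5 | 1.0 | 7.5% | 0.00 | +0.09 | −0.09 | −0.08 |
| 0.7 | 0.5 | 7.5% | 0.00 | +0.07 | −0.07 | −0.04 |
| 0.7 | 1.0 | 7.5% | 0.00 | +0.12 | −0.12 | −0.11 |

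In the last column sham loses more subjects (for example 21.6% against 8.5% in the fourth row), so the bias runs against the device.

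**Reading the largest value.** 0.22/1.5 = 15% of the target; 0.22/0.36 = 0.6 standard errors. It requires g(active) = 0.223/0.15 = 1.5 points. If the true difference were zero, the two-sided 5% error would become Φ(−1.96 + 0.61) + Φ(−1.96 − 0.61) = 0.089 + 0.005, about 9%.

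**Adding the early daily rating.** Where this was computed (second and fourth patterns), the bias fell to 0.00. In these simulations dropout depended only on that rating, so this is the best case.

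**Which daily summary.** The last available week is the obvious choice, but it falls near week 12 for completers and much earlier for early leavers. Suppose dropout is random, the early effect is a fraction f of the final one, and the 3-month change has slope b on the last-week rating among completers. The early leavers' values are then read on the wrong time scale, and the bias is −p × b × 1.5 × (1 − f). With p = 0.15 and b = 0.8 (assumed):
- f = 0.4: −0.15 × 0.8 × 1.5 × 0.6 = −0.11
- f = 0.8: −0.15 × 0.8 × 1.5 × 0.2 = −0.04

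The listed model has no bias in that case. Large-sample simulation agrees (about −0.04 to −0.11), and a window common to all subjects gave zero.

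**The case against.** A reader might infer that the omission favours the device, because those who find it useless leave and are credited with the completers' course. The documents do not support that. It needs poor responders to leave active more selectively than sham, and nothing in the plan says they will. With one lack-of-benefit threshold for both arms, sham loses more subjects and the bias goes the other way. With like selection it cancels.

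The other objections, and what stands of each:

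- **The delta analysis already covers this.** In part. It probes the direction that would flatter the device. But it is secondary, gives no delta values, adjusts active withdrawals only and ignores what those subjects recorded. It cannot show a bias against the device or correct the primary estimate.
- **Pain characteristics might include daily data.** The term is undefined, so this cannot be ruled out. It sits beside demographics and would not naturally cover activity interference or device use.
- **The auxiliaries are flawed.** This stands. Someone who stops wearing the device is told not to rate, so ratings are selectively missing. The zero bias after the addition also owes something to the simulation's own dropout rule. Missing at random may be only partly restored.
- **The effect is small.** Also fair. The power section reports little attrition in earlier work, the plan tries to keep following those who wish to stop, later leavers contribute week-6 data, and most values in the table are well under half a standard error.

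**Conclusion.** The point holds as a weakness in the imputation model, not as a demonstrated bias in a known direction. The listed predictors leave out post-baseline data that probably relate to both dropout and outcome, which makes missing at random harder to defend than it needs to be. Under the stated assumptions the primary difference could move by up to about 0.2 points either way, roughly 15% of the 1.5-point target and 0.6 of the planned standard error. It would not move if selection were alike in both arms. The size rests on assumed correlations, dropout slopes and timing, none of which the documents supply. With a 1.5-point effect and power near 98.5%, the conclusion would rarely turn on it; with a small or null effect it could matter. The change is worth making because it is cheap and is the same whichever way the bias runs.

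**What to change.** Within each arm, add one or two auxiliary summaries to the imputation model, each measured over the same early window for every subject. One example is the mean daily activity-interference rating over days 8-14 (daily pain for pain outcomes), with mean daily device use over the same days. Impute these summaries when they are missing. Do not use the last available 7-day mean, which mixes time points between completers and early leavers. Do not enter the whole daily series, which would overfit with about 50 observed subjects per arm. Define pain characteristics. Keep the delta analysis, since the auxiliaries may restore missing at random only in part. If the sponsor prefers to leave these data out, the plan should say why.

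Cost: plan wording and a little extra programming, with no new data collection.
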